as local pain, irritation, or rash localized at sites of known or suspected tumor), Grade 3 rash, Grade 3 immune-related adverse event (irAE, defined below) that resolves to a Grade 1 or less within 28 days, or a transient (resolving within 6 hours of onset) Grade 3 infusion-related adverse event. A Grade 3 irAE that resolves to a Grade 1 or less within 28 days, while not constituting a DLT, may preclude further administration of NIVOLUMAB or NIVOLUMAB with ipilimumab to the subject. Grade 2 irAEs may require skipping a dose unless resolved to grade 1 or less at the time of drug administration. Version 4.0 of the NCI Common Terminology Criteria for Adverse Events (CTCAE) will be utilized for AE reporting. Version 4.0 of the CTCAE is identified and located on the CTEP website at http://ctep.cancer.gov/protocolDevelopment/electronic_applications/ctc.htm. All appropriate treatment areas should have access to a copy of Version 4.0 of CTCAE).

Toxicities occurring more than 28 days after the first dose will be monitored and discussed with BMS.

Immune-Related Adverse Events

An irAE is defined as a clinically significant adverse event of any organ that is associated with either study drug exposure, of unknown etiology, and is consistent with an immune-mediated mechanism. Appropriate efforts should be made to rule out neoplastic, infectious, metabolic, toxin, or other etiologic causes of the irAE.

Given the intended mechanism of action of NIVOLUMAB and ipilimumab, particular attention will be given to adverse events that may follow enhanced T-cell activation such as dermatitis and colitis, or other irAEs.

Immunology

Blood and peripheral blood mononuclear cell samples will be collected and evaluated by leukapheresis or peripheral blood draw for flow cytometry (T cell, B cell, NK, monocytes, CD3, CD4, CD8, CD4/CD8, CD11b, CD11c, CD14, CD20, CD25, CD33, CD56, CD69, CD71, CD73, CD80, CD127, FOXP3, LAG3, TIGIT, BTLA, Tim3, CTLA-4, PD-1, PD-L1, CD244, OX-40, 41-BB, CD40, CD4/MHC Class II positive cells, and CD8/MHC Class II positive cells), serum cytokines (IL-6, IL-10, TNF- β , ING-gamma, TGF- β , neopterin and sIL-2R), cellular immune function (tetramer and/or ELISpot assays utilizing melanoma and other control antigens).

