4.2. Treatment Regimen

4.2.1 Toxicity management

4.2.1.1. Management:

For Grade 1 and 2 adverse events felt due to NIVOLUMAB or NIVOLUMAB with ipilimumab, symptomatic treatment is called for generally without a dose delay. For selected irAEs of grade II, especially colitis and ophthalmologic toxicity, one dose of NIVOLUMAB or NIVOLUMAB with

ipilimumab may be skipped until resolution of the toxicity to Grade 1 or less. Grade 3 irAEs that constitute dose limiting toxicity will cause treatment with NIVOLUMAB or NIVOLUMAB with ipilimumab to be discontinued permanently. For grade III irAEs that do not constitute DLT, do not require more than 2 weeks of systemic steroid treatment, and resolve within 28 days to grade I or less, with either one or no skipped doses, therapy with NIVOLUMAB or NIVOLUMAB with ipilimumab may continue at the same dose(s). There will be no dose reductions of NIVOLUMAB for an individual patient. Management of infusion reactions is defined in section 5.2.2 below.

4.2.1.2. Dose Delay:

NIVOLUMAB with ipilimumab administration should be delayed for the following:

- Any Grade ≥ 2 non-skin, drug-related adverse event, with the following exceptions:
 - Grade 2 drug-related fatigue or laboratory abnormalities do not require a treatment delay
- Any Grade 3 skin, drug-related adverse event
- Any Grade 3 drug-related laboratory abnormality, with the following exceptions for AST, ALT, total bilirubin, amylase and lipase:
 - If a subject has a baseline AST, ALT, or total bilirubin that is within normal limits, delay dosing for drug-related Grade ≥ 2 or greater toxicity
 - If a subject has baseline AST, ALT, or total bilirubin within the Grade 1 toxicity range, delay dosing for drug-related Grade ≥ 3 or greater toxicity
 - Grade 3 amylase or lipase abnormalities that are not associated with symptoms or clinical manifestations of pancreatitis do not require a dose delay. It is recommended to consult with the BMS Medical Monitor for Grade 3 amylase or lipase abnormalities.
- Any adverse event, laboratory abnormality, or intercurrent illness which, in the judgment of the investigator, warrants delaying the dose of study medication.

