Because of the potential for clinically meaningful nivolumab or ipilimumab related AEs requiring early recognition and prompt intervention, management algorithms have been developed for suspected pulmonary toxicity, GI, hepatotoxicity, endocrinopathy, skin toxicity, neurological toxicity and nephrotoxicity. For the overlapping adverse event management algorithms present in both the NIVOLUMAB and ipilimumab IB (**GI, hepatic, and endocrine** algorithms), the recommendations are to follow the NIVOLUMAB IB adverse event algorithms as opposed to the ipilimumab IB algorithms.

Subjects may resume treatment with study drug (s) when the drug-related AE(s) resolve to Grade 1 or baseline value, with the following exceptions:

- Subjects may resume treatment in the presence of Grade 2 fatigue

-
- Subjects who have not experienced a Grade 3 drug-related skin AE may resume treatment in the presence of Grade 2 or less skin toxicity
 - Subjects with baseline Grade 1 AST/ALT or total bilirubin who require dose delays for reasons other than a 2-grade shift in AST/ALT or total bilirubin may resume treatment in the presence of Grade 2 AST/ALT OR total bilirubin
 - Subjects with combined Grade 2 AST/ALT AND total bilirubin values meeting discontinuation parameters should have treatment permanently discontinued
 - Drug-related pulmonary toxicity, diarrhea, or colitis, must have resolved to baseline before treatment is resumed
 - Drug-related endocrinopathies adequately controlled with only physiologic hormone replacement may resume treatment

If the criteria to resume treatment is met, the subject should restart treatment at the next scheduled timepoint per protocol. However, if the treatment is delayed past the next scheduled timepoint per protocol, the next scheduled timepoint will be delayed until dosing resumes. If treatment is delayed greater than 6 weeks, the subject must be permanently discontinued from study treatment, except as specified in the discontinuation section below.

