4.2.1.3. Discontinuation

Treatment should be permanently discontinued for the following:

- Any Grade 2 drug-related uveitis or eye pain or blurred vision that does not respond to topical therapy and does not improve to Grade 1 severity within the re-treatment period OR requires systemic treatment
- Any Grade 3 non-skin, drug-related adverse event lasting > 7 days, with the following exceptions for drug-related laboratory abnormalities, uveitis, pneumonitis, bronchospasm, diarrhea, colitis, neurologic toxicity, hypersensitivity reactions, and infusion reactions:
- Grade 3 drug-related uveitis, pneumonitis, bronchospasm, diarrhea, colitis, neurologic toxicity, hypersensitivity reaction, or infusion reaction of any duration requires discontinuation

Grade 3 drug-related laboratory abnormalities do not require treatment discontinuation except:

- Grade 3 drug-related thrombocytopenia > 7 days or associated with bleeding requires Discontinuation
- Any drug-related liver function test (LFT) abnormality that meets the following criteria require discontinuation:
 - AST or ALT > 8 x ULN
 - Total bilirubin > 5 x ULN

-
- Concurrent AST or ALT > 3 x ULN and total bilirubin > 2 x ULN
 - Any Grade 4 drug-related adverse event or laboratory abnormality, except for the following events which do not require discontinued.
 - Isolated Grade 4 amylase or lipase abnormalities that are not associated with symptoms or clinical manifestations of pancreatitis. It is recommended to consult with the BMS Medical Monitor for grade 4 amylase or lipase abnormalities.
 - Isolated Grade 4 electrolyte imbalances/abnormalities that are not associated with clinical sequelae and are corrected with supplementation/appropriate management within 72 hours of their onset
 - Dosing interruptions to allow for prolonged steroid tapers to manage drug-related adverse events are allowed. Prior to re-initiating treatment in a subject with a dosing interruption lasting > 6 weeks, the BMS medical monitor must be consulted. Tumor assessments should continue as per protocol even if dosing is interrupted.
 - Dosing interruptions > 6 weeks that occur for non-drug-related reasons may be allowed if approved by the BMS medical monitor. Prior to re-initiating treatment in a subject with a dosing interruption lasting > 6 weeks, the BMS medical monitor must be consulted. Tumor assessments should continue as per protocol even if dosing is interrupted.

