Management algorithms for high-grade irAEs have been established for ipilimumab, where timely application of defined immunosuppressive regimens appear to be effective in limiting the morbidity and mortality from such events without compromising therapeutic efficacy. A general management algorithm with recommended guidelines for the treatment and monitoring of suspected irAEs, as well as algorithms for specific irAEs (ie, diarrhea/colitis, endocrinopathy, hepatotoxicity, and neuropathy) are provided in the NIVOLUMAB Investigator Brochure. **All incidents of diarrhea should be managed according to the diarrhea/colitis algorithm.** Additional clinical experience will be required to define the spectrum of irAE-like events that may emerge in the NIVOLUMAB program, and these algorithms are useful guides towards establishing an effective management approach as experience accumulates.

In all cases, study drug-related \geq Grade 2 diarrhea/colitis will be managed with regular communication between the Investigator and BMS, and with a minimum of at least 1 in-person visit per week until the diarrhea/colitis is $<$ Grade 2. Any Grade 2 adverse event of colitis (per Version 4.0 CTCAE) that also results in additional medical requirements, such as more than 2 weeks of immunosuppressive doses of steroids ($>$ 10 mg/day of prednisone or equivalent), blood transfusion, or i.v. hyperalimentation, will be defined as a Grade 3 adverse event. Subjects are to be carefully monitored until recovery of the colitis to \leq Grade 1.

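### Section 4.2.1.1 and the synopsis imply that dosing may proceed once Grade 2 colitis is Grade 1 or less, 4.2.1.2 requires baseline, and nothing ranks the sections

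*Combined protocol and SAP*

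**What the plan says.** Four places in the combined protocol and SAP bear on dosing after drug-related colitis.

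- **Section 4.2.1.1 (Management).** Grade 1 and 2 events are treated symptomatically, as a rule with no delay. An exception follows: "For selected irAEs of grade II, especially colitis and ophthalmologic toxicity", where one dose of nivolumab or of nivolumab with "ipilimumab may be skipped until resolution of the toxicity to Grade 1 or less". The section also lets therapy go on at the same dose after a Grade 3 immune-related event that is not a DLT, needs no more than 2 weeks of systemic steroids, settles to Grade 1 or less within 28 days and costs at most one dose. It makes no exception for colitis there.
- **Synopsis (Dose-limiting Toxicity).** "Grade 2 irAEs may require skipping a dose unless resolved to grade 1 or less at the time of drug administration". This sentence does not name colitis, but the synopsis gives colitis as an example of an immune-related event.
- **Section 4.2.1.2 (Dose Delay).** Dosing should be delayed for any non-skin drug-related event of Grade 2 or higher, apart from Grade 2 fatigue and certain laboratory findings. The general resume rule is "Subjects may resume treatment with study drug (s) when the drug-related AE(s) resolve to Grade 1 or baseline value, with the following exceptions". One of the listed exceptions is "Drug-related pulmonary toxicity, diarrhea, or colitis, must have resolved to baseline before treatment is resumed".
- **Section 4.2.1.3 (Discontinuation).** "Grade 3 drug-related uveitis, pneumonitis, bronchospasm, diarrhea, colitis, neurologic toxicity, hypersensitivity reaction, or infusion reaction of any duration requires discontinuation".

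**The concern.** Safety and tolerability are the primary objective, and section 6.10 makes colitis of Grade 2 or higher an event of special interest. The re-dosing rule for this toxicity should be the same wherever the treating physician looks it up. Here the section headed Management and the synopsis both point to Grade 1 or less, while the resume criteria in 4.2.1.2 demand baseline. A physician working from 4.2.1.1 or the synopsis could give the next dose to a subject with residual Grade 1 colitis and so breach a mandatory criterion of the same protocol.

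Two further mismatches between 4.2.1.1 and the sections after it make it harder to assume that 4.2.1.1 is meant to yield to them. One concerns whether a Grade 2 event calls for a delay at all. The other concerns whether treatment may continue after Grade 3 colitis. Dose-delay and tolerability data could also come to depend on which section was followed.

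**Working it through.** No arithmetic applies, and the plan states no figure on this point. The check is a comparison of the texts.

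**1. Resumption after Grade 2 drug-related colitis**

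| Baseline grade | Grade on dosing day | 4.2.1.1 and synopsis (implied) | 4.2.1.2 | Agree? |
|---|---|---|---|---|
| 0 | 0 | dose | dose | yes |
| 0 | 1 | dose | withhold | **no** |
| 1 | 1 | dose | dose (at baseline) | yes |
| 0 or 1 | 2 | threshold not met | withhold | see step 2 |

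On resumption, the thresholds part by one grade, and only for a subject who started at Grade 0. That is probably the usual starting point, because exclusion criterion 8 allows the investigator to exclude underlying conditions associated with diarrhea. This is an inference; the plan does not state it.

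**2. Delay at Grade 2.** Section 4.2.1.1 sets no delay as the norm and makes skipping optional even for colitis. Section 4.2.1.2 says that dosing should be delayed for a non-skin drug-related event of this grade. Colitis is not among its exceptions.

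**3. Continuation after Grade 3.** Take Grade 3 colitis that is not a DLT, needs no more than 2 weeks of systemic steroids, falls to Grade 1 or less within 28 days and costs no more than one dose. Under 4.2.1.1 therapy may continue. Under 4.2.1.3 it must stop, however brief the episode.

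Section 6.10 adds to this group by counting Grade 2 colitis as Grade 3 when it brings extra medical requirements, "such as more than 2 weeks of immunosuppressive doses of steroids" being one example. Upgrading for that steroid reason would fail the steroid condition in 4.2.1.1. Upgrading for a transfusion or intravenous feeding would not in itself fail it.

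**4. Is there a ranking?** The colitis exception in 4.2.1.2 qualifies the resume sentence that introduces it. It does not mention 4.2.1.1 or the synopsis, and neither of them mentions it. The one precedence statement on managing adverse events, in 4.2.1.2, puts the nivolumab Investigator Brochure algorithms ahead of the ipilimumab ones. It does not rank protocol sections.

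**5. Do other provisions settle the threshold?**

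- Section 4.6.1 requires steroids given for immune-related events to be at 10 mg/day of prednisone or less for at least 2 weeks before the next dose. It bites only where systemic steroids were used.
- Section 4.2.1.2 lets the investigator delay a dose on judgment, which is discretionary.
- Section 6.10 requires weekly visits and regular contact with the company until the event is below Grade 2, so that duty ends where the disagreement begins. Its recovery point of Grade 1 or less concerns monitoring, not dosing.
- Section 6.10 also says "All incidents of diarrhea should be managed according to the diarrhea/colitis algorithm". That algorithm is in the nivolumab Investigator Brochure, which is not among the documents, so whether it sets a resume threshold cannot be checked.

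None of these, as written here, says which threshold governs.

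**The case against.** The best reply is that the texts can be read together. Section 4.2.1.1 and the synopsis speak of when a dose may be skipped; neither says outright that a subject may be dosed at Grade 1. Section 4.2.1.2 holds the actual resume criteria and takes colitis out of the general threshold in mandatory terms. On an ordinary reading a specific mandatory rule controls a permissive one. The trial also has a single center and a sponsor-investigator, so sites cannot diverge, and colitis of Grade 2 or higher must be notified rapidly to the company. The brochure algorithm may give the answer.

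Much of this stands. The permission is implied, a careful reader would probably follow the stricter rule, and the practical risk is limited. It does not remove the inconsistency. Section 4.2.1.1 is not merely general, since it singles out colitis, and the mismatches on delay and on Grade 3 show that it was not aligned with the later sections.

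A reader might be tempted by readings that the documents do not support:

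- *That the plan authorizes re-dosing at residual Grade 1.* It does not say so; it only implies it.
- *That the problem is confined to Grade 2 colitis because 4.2.1.3 settles Grade 3.* Section 4.2.1.1 conflicts with 4.2.1.3 as well, and nothing ranks those two sections either.
- *That the investigator has no answer at all.* The brochure cannot be seen, so the most that can be said is that these documents give none.

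**Conclusion.** The inconsistency is real and modest. Section 4.2.1.1 and the synopsis imply a looser resume threshold for colitis than 4.2.1.2 imposes. Section 4.2.1.1 is also looser than 4.2.1.2 on delay at Grade 2 and looser than 4.2.1.3 on continuation after Grade 3.

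No effect size can be given, because the documents do not report how often residual Grade 1 colitis is present on a dosing day. One course of action, waiting for baseline and discontinuing at Grade 3, complies with every text. The DLT definition, the stopping rules and the planned statistics are untouched, so a reader should not infer any flaw in the safety analysis itself.

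The conclusion rests on reading the Grade 1 wording in 4.2.1.1 and the synopsis as marking when dosing may proceed, and on the absence of any ranking sentence in the documents supplied.

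**What to change.** In 4.2.1.1 and in the synopsis, state that 4.2.1.2 governs dose delay and resumption and that 4.2.1.3 governs permanent discontinuation. In the same two places, except drug-related diarrhea, colitis and pulmonary toxicity from the Grade 1 threshold and say that return to baseline is required.

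The cost is a sentence or two in each place, made through a protocol amendment. Some subjects may wait longer for a dose or miss one, but 4.2.1.2 already requires that. For Grade 3 diarrhea or colitis, the change only confirms what 4.2.1.3 already demands.

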3.4.6 Early Discontinuation Criteria and Procedures

3.4.6.1 Discontinuation of Study Drug

It is the right and duty of the Investigator to discontinue the study drugs of any subject if he feels that discontinuation of the study drugs is necessary to protect the subject, or that there are unmanageable factors that may interfere significantly with the study procedures and/or the interpretation of results.

Administration of the study drugs will be discontinued if the subject develops a DLT, documented relapse, or other intolerability to the study drugs.

Administration of the study drugs may be discontinued during the study for any of the following reasons:

- Adverse event(s)
- Protocol violation
- Subject withdrew consent
- Lost to follow-up
- Other
- Death

For subjects who discontinue the study drugs for any reason, the remaining study visits and associated evaluations (without dosing) should be completed. Patients who discontinue the study drug(s) due to a toxicity will be followed until the toxicity resolves to baseline. Patients will continue to be followed on the protocol schedule for radiology assessments and for relapse free survival. Pharmacokinetic samples will only be collected at the visit following study drug discontinuation.

All subjects will be followed for adverse events for at least 70 days after the last dose of study drugs and for survival follow-up indefinitely until withdrawal of consent or death.

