4.2.4.1. Definition

A DLT is defined as a NIVOLUMAB or NIVOLUMAB with ipilimumab related Grade 3 or greater adverse event other than the exceptions noted occurring within 29 days after the first dose excluding: Grade 3 adverse event of tumor flare (defined as local pain, irritation, or rash localized at sites of known or suspected tumor), Grade 3 rash, Grade 3 immune-related adverse event (irAE, defined below) that resolves to a Grade 1 or less within 28 days, or a transient (resolving within 6 hours of onset) Grade 3 infusion-related adverse event. A Grade 3 irAE that resolves to a Grade 1 or less within 28 days, while not constituting a DLT for dose escalation purposes, may preclude further administration of NIVOLUMAB and/or ipilimumab to the subject.

The following are excluded from the definition of a DLT:

- Grade 3 rash,
- Grade 3 irAE that resolves to a Grade 1 or less within 28 days, or
- A transient (resolving within 6 hours of onset) Grade 3 infusion-related adverse event.

A Grade 3 irAE that resolves to a Grade 1 or less within 28 days, while not constituting a DLT, may preclude further administration of the study drugs to the subject. A DLT will be considered related to 1 or both study drugs unless there is a clear, well-documented, alternative explanation for the toxicity.

Toxicities occurring more than 28 days after the first dose will be monitored and discussed with BMS.

All adverse events that meet DLT criteria, as well as any Grade 3 or 4 infusion reactions whether or not the event is a DLT, must be reported using the rapid notification procedures described in Section 9.6.

Patients who discontinue treatment for toxicities will continue on the protocol radiology evaluation schedule every 12 weeks once the toxicity resolves to obtain relapse-free survival data.

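### For a clinical endocrinopathy that stays Grade 3 beyond 7 days and is controlled on hormone replacement, 4.2.1.2 allows treatment to resume while 4.2.1.3 ends it, and the DLT definition does not say whether such an event has resolved

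*Combined protocol and SAP*

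**What the plan says.** Four parts of the protocol bear on the same patient.

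- **4.2.1.2 (Dose Delay), criteria to resume.** The general rule is "Subjects may resume treatment with study drug (s) when the drug-related AE(s) resolve to Grade 1 or baseline value, with the following exceptions". One of the listed exceptions is "Drug-related endocrinopathies adequately controlled with only physiologic hormone replacement may resume treatment". The fatigue, skin and liver-test exceptions beside it mention grades; this one does not.
- **4.2.1.3 (Discontinuation).** Treatment ends permanently for "Any Grade 3 non-skin, drug-related adverse event lasting > 7 days, with the following exceptions for drug-related laboratory abnormalities, uveitis, pneumonitis, bronchospasm, diarrhea, colitis"; the list continues with neurologic toxicity, hypersensitivity and infusion reactions. Endocrinopathy does not appear. For laboratory findings the section adds "Grade 3 drug-related laboratory abnormalities do not require treatment discontinuation except", followed by platelet and liver-test criteria.
- **4.2.1.1 (Management).** A Grade 3 irAE that is a DLT ends treatment. One that is not a DLT may continue at the same dose if it needs no more than 2 weeks of systemic steroids and manages to "resolve within 28 days to grade I or less, with either one or no skipped doses".
- **4.2.4.1 and the synopsis (DLT definition).** Related events of Grade 3 or more within 29 days of first dose are DLTs, apart from listed exclusions. One exclusion is "Grade 3 irAE that resolves to a Grade 1 or less within 28 days, or" a transient infusion event. Neither place mentions hormone replacement. Section 3.4.6.1 then says "Administration of the study drugs will be discontinued if the subject develops a DLT, documented relapse, or other intolerability to the study drugs", and 4.2.5 counts DLTs toward a halt in accrual.

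**The concern.** The resume exception in 4.2.1.2 is written for events that are controlled without having returned to Grade 1 or baseline. If such an event is Grade 3 and lasts more than 7 days, the next subsection ends treatment permanently. Two investigators following the protocol in good faith could record the same patient differently, one as continuing on drug and the other as a permanent discontinuation for toxicity.

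This bears on the primary objective, safety and tolerability (1.5), in a trial that 1.4.3 says is meant to add feasibility and toxicity experience with this regimen. Endocrine events are foreseen: 2.4.2 and 6.10 name the endocrine system among the four sites that ipilimumab irAEs most often involve. The DLT question also matters because the halting rule in 4.2.5 acts on small counts.

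**Working it through.** The plan states no figure that this point could reproduce. The main check is a comparison of the rules, followed by two short calculations of scale.

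**1. The rules side by side, for a clinical drug-related endocrinopathy controlled on physiologic replacement**

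| Case | 4.2.1.2 | 4.2.1.3 | 4.2.1.1 |
|---|---|---|---|
| Grade 2 | may resume | 7-day rule not triggered | Grade 3 test not triggered |
| Grade 3 for 7 days or less | may resume | 7-day rule not triggered | depends on its own conditions |
| Grade 3 for more than 7 days, Grade 1 or less within 28 days | may resume | discontinue | may continue, if the steroid and skipped-dose limits are met |
| Grade 3 for more than 7 days, not Grade 1 or less within 28 days, not a DLT | may resume | discontinue | condition for continuing not met |
| As the previous row, onset within 29 days | may resume | discontinue | DLT: discontinue |

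In the last three rows 4.2.1.2 and 4.2.1.3 give opposite outcomes. In the third row 4.2.1.1 also disagrees with 4.2.1.3, and that disagreement covers other non-skin Grade 3 irAEs to which the 7-day rule applies. A purely laboratory Grade 3 finding may escape through the laboratory exception, so it is left out.

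**2. Is precedence stated?** Section 4.2.1.2 defers to discontinuation in two places only: combined AST/ALT and bilirubin values that meet discontinuation parameters, and delays over 6 weeks. The endocrine exception has no such wording.

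**3. Effect on a discontinuation rate.** With 20 patients, one patient classified differently moves the rate by 1/20 = 5 percentage points. To show this against sampling error, 17/20 = 85% has an exact (Clopper-Pearson) 95% interval of 62% to 97%, and 16/20 = 80% has 56% to 94%. The 17 of 20 is the predecessor cohort's result in 1.4.3, used here only as a convenient starting value.

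**4. The DLT definition.** It refers to neither the resume rule nor the 7-day rule. What it leaves open is whether a Grade 3 event controlled on replacement has resolved to Grade 1 or less. If the answer is no and onset was within 29 days, the event is a DLT, treatment ends (4.2.1.1, 3.4.6.1) contrary to 4.2.1.2, and it counts in 4.2.5.

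To gauge that, I computed the exact binomial probability of crossing 4.2.5: at least 3 of the first 6, at least 4 of the first 10, or at least 0.40 × 20 = 8 of 20. Both rates below are assumptions, since the documents give neither. The columns show the percentage points added to the DLT rate if such events are counted as unresolved.

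| Assumed DLT rate from other causes | +0 | +2 | +5 | +10 |
|---|---|---|---|---|
| 5% | 0.3% | 0.8% | 2.2% | 7.3% |
| 10% | 2.2% | 3.8% | 7.3% | 16.2% |
| 15% | 7.3% | 10.4% | 16.2% | 28.8% |
| 20% | 16.2% | 20.9% | 28.8% | 44.1% |

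Check on the first look: P(at least 3 of 6 at 10%) = 0.0159.

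**The case against.** The strongest reply is that the sections form a sequence. Section 4.2.1.3 lists what ends treatment; 4.2.1.2 is permissive and governs return from a delay. A patient already discontinued never reaches the resume criteria, and the endocrine exception still has work to do for Grade 2 events, which 4.2.1.2 otherwise delays. This is a workable reading, but the protocol does not state it. The two express deferrals in 4.2.1.2 invite the opposite inference where deferral is absent.

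A second reply is that frequency cannot be shown. Whether an event on replacement keeps its Grade 3 depends on CTCAE, and 4.2.1.2 sends endocrine management to the nivolumab Investigator Brochure algorithm; neither is in the documents. Sections 2.4.2 and 6.10 also describe ipilimumab irAEs as usually low grade and more common after several doses, whereas Table 1 places only the Day 1 and Day 22 doses inside the DLT window. This stands. It limits the expected number of cases but does not remove the contradiction.

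A reader might go further and infer that DLT counts depend on whether 4.2.1.2 or 4.2.1.3 is followed. They do not. The DLT definition is separate from both, and its irAE exclusion is the same in the synopsis and 4.2.4.1. The DLT problem is an ambiguity inside that definition.

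**Conclusion.** The contradiction is real and narrow. It concerns a clinical drug-related endocrinopathy that remains Grade 3 for more than 7 days and is controlled with physiologic replacement. Whether that patient counts as a toxicity discontinuation depends on the subsection applied, at 5 points per patient in 20. The number of such patients is unknown and may be zero.

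The DLT ambiguity is a separate, smaller matter, confined to onset within 29 days. The probabilities above are illustrations under assumed rates, not estimates for this trial.

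Two further inferences are not supported. The conflict does not arise for every Grade 3 endocrinopathy: an event that falls below Grade 3 within 7 days does not trigger the 7-day rule, and a purely laboratory finding may be excepted. Nor do the documents support a projected large fall from the predecessor cohort's 17 of 20. That would require assuming several such patients, and it treats a comparison with that cohort as a planned analysis. Section 6.3.3 plans descriptive safety summaries, and the predecessor comparison in 6.3.4 concerns T-cell proliferation.

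The point is worth correcting because it touches the primary objective and costs little.

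**What to change.** Reconcile 4.2.1.1, 4.2.1.2 and 4.2.1.3 so that one rule governs a Grade 3 endocrinopathy controlled on hormone replacement, and repeat it identically in each, including the exception list of 4.2.1.3. In the same edit, settle how the 28-day test in 4.2.1.1 and the 7-day test in 4.2.1.3 relate for other Grade 3 non-skin irAEs. In the synopsis and 4.2.4.1, state how resolution to Grade 1 or less is judged for an event on replacement, and make the consequence agree with the resume rule. Which clinical rule applies is for the sponsor to decide.

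The cost is wording in four subsections and the synopsis, through a written amendment with the approvals that 12.2 requires. No patients, procedures or data are added.
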